6.0 PROTOCOL DESCRIPTION

Patient informed consent

The investigator is responsible for obtaining informed consent from each prospective study patient prior to the performance of any study related procedures. After a patient has been provided with the information of the study and given time to think on whether to participating into the study, the patient will be asked to sign and date a consent form. One copy of the signed patient consent form must be handed out to the patient and one must be filed by the investigator in the investigator files. After the patient and the investigator have signed and dated the consent form, the study data collection process may start.

Patients meeting all the inclusion criteria and not meeting any of the exclusion criteria are eligible for the study. Data will be collected at the following study visits:

Enrollment

Noninvasive electrical activation and acute hemodynamic study

Implant

[figure not shown]
Pre-discharge (PDH) (\leq 72 hours post implant)

Month 3 follow-up visit: 90 ± 14 days post implant

Month 6 follow-up visit: 180 ± 14 days post implant

Table 1. Data collection for each scheduled visit

	Enrollment	Implant *	PDH*	Month 3	Month 6
Patient Informed Consent	x				
Echocardiogram	x		x	x	x
Medical History	x				
Cardiovascular Medication	x	x	x	x	x
NYHA Class	x			x	x
6MHW	x			x	x
SF-36QoL	x			x	x
12-lead electrocardiogram	x	x		x	x
Cine images		x			
Device Interrogation		x	x	x	x
Adverse Event	x	x	x	x	x
Protocol Deviation	x	x	x	x	x

Figure 1. Study Flow Chart

Noninvasive mapping of electrical activation

Ventricular activation maps will be acquired simultaneously with hemodynamic measurements using noninvasive mapping system (ECVUE, Medtronic Inc, USA). A thoracic computed tomographic scan will be acquired with the electrodes attached to the patient. Local ventricular activation times will be defined as the onset of the QRS complex or the pacing spike to the maximal negative slope of each unipolar electrogram.

The following electrical dyssynchrony indices will be derived

- i) Total activation time (TAT) is defined as the time difference between the earliest and latest site of activation on the entire ventricular epicardium (LV and RV);
- ii) RVTAT is defined as the time difference between the earliest and latest site of activation on the RV ventricular epicardium;
- iii) LVTAT is defined as the time difference between the earliest and latest site of activation on the LV ventricular epicardium;
- iv) Ventricular electrical uncoupling (VEU) is defined as mean LV activation time minus mean RV activation time (LVTAT-RVTAT)
- v) Intra-LV electrical dyssynchrony index (ED) is the standard deviation of activation times at 500 sites on the LV epicardium, including the epicardial aspect of the septum.

Placement of electrophysiology catheters for CRT delivery

Pacing leads will be placed in high right atrium, His-bundle region, right ventricular apex, high septal RV, coronary sinus posterior/lateral branch, coronary sinus anterior branch, lateral and septal region of endocardial LV in order to deliver CRT in 8 different configurations as stated below:

- 1) Conventional biventricular pacing with RV lead in right ventricular apex and LV lead in lateral or posterior branch of coronary sinus
- 2) Biventricular pacing with the LV lead in coronary sinus in closest possible proximity to the latest electrical activation region (18 region) if it is different to the site tested in (1)
- 3) Direct His-bundle pacing
 - i) His bundle pacing catheter distal tip as cathode and RV lead proximal pole as anode
 - ii) His bundle pacing catheter distal tip as cathode and proximal pole of LV lead placed in lateral or posterior branch of coronary sinus as anode.
 - iii) His bundle pacing catheter distal tip as cathode and His bundle pacing catheter proximal pole as anode.

In subjects in sinus rhythm

- i) together with RV bipolar pacing with RV lead in RV apex.

In subjects in AF

- i) together with RV bipolar and LV bipolar pacing

4) Multi-point pacing

- i) Triple site pacing with two RV leads in the RV apex and high RV septum and LV lead in posterior or lateral branch of coronary sinus.
- ii) Triple site pacing with RV lead in the RV apex and one LV lead in posterior or lateral branch of coronary sinus and the other LV lead in anterior branch of coronary sinus.
- iii) Triple site pacing with RV lead in RV apex and one quadripolar LV lead in posterior or lateral branch of coronary sinus and pacing at 2 sites simultaneously from the quadripolar lead.

During delivery of CRT the output will be set at twice the capture threshold and pacing impulse will be delivered in VDD mode with an AV delay of 80msec and VV delay at 0msec for all leads in the ventricles.

Acute hemodynamics studies

Invasive LV hemodynamic measurements of LV dP/dt will be recorded using a micromanometer (Radi Medical Systems, St Jude Medical, USA) placed in the LV cavity.

All measurements will be made with an average of 10 second recordings with no occurrence of premature atrial or ventricular beats during the recording and 1 minute interval between changes in pacing settings.

During sinus rhythm and the 7 configurations of CRT pacing as stated above both noninvasive electrical activation map and acute hemodynamic measurement will be recorded for analysis.

Implantation of CRT device**1) Conventional pacing configuration**

The CRT system will be implanted with standard technique for conventional pacing configuration. Only market released CRT devices and leads will be implanted.

2) Epicardial LV pacing in the latest activation site

LV lead will be placed in the LV latest activation site or the site in closest proximity to the latest activation site and if necessary quadripolar or active fixation LV lead will be used to achieve stability.

3) Direct His-bundle pacing

i) In subjects in sinus rhythm

For direct-His bundle pacing, standard techniques will be used to place an LV lead preferably in the posterolateral branch of the coronary sinus system, RV and right atrial lead. His pacing lead (SelectSecure, model 3830, Medtronic Inc, USA) supported using a dedicated delivery sheath (model C315, Medtronic Inc, USA) or a deflectable lead delivery sheath (model C304, Medtronic Inc, USA) to the site showing His bundle signal on the mapping catheter. Multiple position to optimize QRS narrowing and threshold could be tested. The His pacing lead and the LV lead will be connected via a Y-adapter (model 5866-38M, Medtronic Inc, USA). The HBP will be connected to the cathode and the LV tip to the anode of the Y-connector.

ii) In subjects in AF

The same as for subjects in sinus rhythm except the His pacing lead will be connected to the atrial port of the CRT device and LV lead into the LV port of the CRT device without the use of a Y adapter.

4) Multiple point pacing

For multiple point pacing, the septal RV and the bipolar LV leads will be connected to the LV port using a parallel Y-adapter (model 2872, Medtronic Inc, USA) for the 2 RV leads group. Whilst the anterior bipolar and posterior/lateral LV lead will be connected using a parallel Y-adapter (model 2872, Medtronic Inc, USA) for the 2 LV leads group. If simultaneous pacing from 2 sites or the quadripolar LV lead pacing is the optimal configuration, a quadripolar lead will be connected to the LV port.

CRT programming

Para meter	Mandatory Device Setting
Mode	DDD or DDDR
Base Rate	≤ 60 min-1
Max. Sensor Rate/Max. Tracking Rate	140 min-1
Mode Switch	"On" if atrial tachyarrhythmia are suspected
Paced AV Delay	150 ms

Sensed AV Delay	120 ms
V-V Delay	0ms

Adverse Events

Definition

Adverse Event (AE) is defined as any untoward medical occurrence in a patient who participates in a clinical investigation. This definition does not imply that there is a relationship between adverse event and the clinical investigation.

Serious Adverse Event (SAE) is defined as an adverse event that

- a) led to death
- b) led to a serious deterioration in the health of the subject that
 - i. resulted in a life-threatening illness or injury
 - ii. resulted in a permanent impairment of a body structure or a body function
 - iii. required in-patient hospitalization or prolongation of existing hospitalization
 - iv. resulted in medical or surgical intervention to prevent permanent impairment to
- c) led to body structure or a body function to foetal distress, foetal death or a congenital abnormality or birth defect.

List of Anticipated Adverse Events

Possible adverse events (in alphabetical order) associated with the acute noninvasive activation mapping and hemodynamic study, include, but are not limited to the following:

- Air embolism
- Allergic reaction
- Arterial or venous occlusion
- Arterial, venous or cardiac perforation
- Asystole
- Bleeding
- Cardiac tamponade
- Death
- Erosion
- Exacerbation of heart failure
- Infection

- Myocardial damage
- Thromboembolism

Possible adverse events (in alphabetical order) associated with the CRT device implantation, include, but are not limited to the following:

Acceleration of arrhythmias (caused by device)
Angina pectoris
Air embolism
Allergic reaction
Asystole
Bleeding
Cardiac tamponade
Chronic nerve damage
Death
Erosion
Exacerbation of heart failure
Excessive fibrotic tissue growth
Extracardiac stimulation (phrenic nerve, diaphragm, chest wall)
Extrusion
Fluid accumulation
Formation of hematomas or cysts
Histotoxic reaction
Infection
Loss of capture
Myocardial damage
Oversensing / undersensing
Palpitations due to documented arrhythmias
Phrenic nerve stimulation
Pneumothorax
Thromboembolism
Venous occlusion
Venous or cardiac perforation

Adverse Events Recording and Reporting

Safety surveillance and reporting will be done for all patients enrolled in the study. This will be started from the time patient provides with the informed consent until the last study visit has been performed or the patient has died or the patient concludes his participation into the study.

All **Serious Adverse Event** is to be documented and reported to the research ethics committee within 24 hours of notification.

As soon as the final details are available for the AE, the information should be reported on the AE case report form:

- Hospitalization details (if applicable)
- Diagnostic test information (if applicable)
- Treatment given (if applicable)
- Final medical diagnosis and cause
- Patient condition
- Final AE status
- Seriousness of AE based on final medical diagnosis and cause
- Relationship of AE to clinical investigation based on final medical diagnosis and cause

Study Termination

All reasonable efforts should be made to retain the patient in the clinical investigation until completion of the clinical investigation.

If a patient concludes their participation in the study, the future care and management will not be affected, whether it is voluntary or otherwise:

- A patient completes the study (Month 6 follow-up).
- A patient / family member may request to withdraw from the clinical investigation at any time with no effect to the patient's present care.
- A patient dies.
- An investigator may withdraw a patient from the study at any time as according to the best interest to the patient.

Risks associated with Participation in the Clinical Investigation

The risks involved with this study are comparable to those associated with the implant of any CRT.

The additional risks are related to the computerized tomography of the heart with possible complication of contrast injury to kidney and allergic reaction. Other additional risks are related to pre-implantation electrical activation study which involves putting in pacing catheters and pressure monitoring catheters in the body with possible risk of injury to the heart, blood vessel, bleeding, wound complications and infection.

Risk Minimization Actions

Additional risks may exist. Risks can be minimized through compliance with this CIP, performing procedures in the appropriate hospital environment, adherence to subject selection criteria, close monitoring of the subject's physiologic status during research procedures and/or follow-ups.

Anticipated Benefits

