The quest to improve CRT responder rate has been subject of intense research interest. Apart from screening for subgroup of heart failure patients with better responder rate to conventional CRT, another possibility is to improve the efficacy of current CRT delivery system. There are two major approaches that have been studied to improve CRT delivery namely selecting the optimal site for LV pacing and alternate method of CRT delivery other than pacing at single epicardial LV site. Study have demonstrated that targeting the LV lead to the site of latest mechanical contraction as determined by strain echocardiogram improved the responder rate.²⁴ Other studies looks into local electrogram guided placement of LV lead to the latest electrically activated segment inside coronary sinus branch.²⁵ Regarding alternate way of CRT delivery, there are interests in using direct His-bundle pacing to overcome the longitudinal conduction delay in the His-Purkinje system. It has been shown that significant narrowing of QRS duration and favorable clinical outcome when compare to conventional CRT can be achieved with direct His-bundle pacing.²⁶ Intuitively, direct-His bundle pacing may provide benefit over pre-excitation of the left ventricle by conventional CRT in patients with right bundle branch block (RBBB) pattern of conduction disturbance. Other potential method to improve CRT outcome is the delivery of multipoint pacing (two LV sites together with one RV site and two RV sites together with one LV site) by recruiting more myocardium to contract simultaneously.²⁷⁻²⁹ Pacing the LV endocardium as compared to epicardium via a coronary access has been shown to improve acute hemodynamic response but however there is no long-term clinical result of endocardial LV pacing comparing to epicardial LV pacing.³⁰

The ability to deliver CRT using different configuration provides opportunity to tailor made resynchronization therapy to heterogenous group of patient in terms of activation delay. This is in contrary to the current concept of a single configuration of CRT deliver suit all patients with widening of QRS duration disregard of pattern of activation delay. Hence the aim of our study is to

investigate whether there is an optimal configuration of CRT delivery that varies between patients with different pattern of activation delay.

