Previous study on noninvasive activation pattern has shown that responders showed higher degree of baseline dyssynchrony and greater improvement of dyssynchrony by CRT when compared to nonresponders.¹⁷⁻¹⁹ The optimal configuration of CRT delivery is defined by that result in the greatest improvement of electrical dyssynchrony. The acute change in electrical dyssynchrony indices will be compare between the optimal configuration and the conventional configuration, namely biventricular pacing with single LV lead in posterior or lateral branch of coronary sinus. A significant different between the two configurations would suggest that there indeed is an optimal configuration of CRT delivery and a tailor made strategy is feasible. To prove this concept of tailor made strategy, devices will be implanted to deliver CRT using the optimal configuration determined by noninvasive electrical activation mapping in non-LBBB patients. The medium term improvement of surrogate marker of LV systolic volume will be compared to that of a predefined level of 40%.

Our group has been using echocardiogram to study mechanical dyssynchrony in patients with heart failure and pacing induced LV dysfunction in predicting response to CRT.³¹⁻⁴⁷ However, in subsequent multi-center trial studying 12 different echocardiographic parameters of mechanical dyssynchrony in predicting CRT response, no single echocardiographic measure of dyssynchrony was shown to improve patient selection for CRT.⁴⁸ The results of the study further strengthen the concept that the response to conventional CRT therapy cannot be predicted by baseline dyssynchrony pattern. It is rather the degree of improvement from baseline that will predict response to CRT therapy. The degree of dyssynchrony improvement on the other hand is determined by the interaction of baseline electrical substrate and the activation change brings about by CRT. The electrical substrate is fixed but different configuration of CRT delivery, including different location of LV lead, can produce different changes in activation. In order to study the interaction of electrical substrate and change in activation brings about by CRT, a tool that allows global electrical mapping of both the LV and RV is considered to be important not only to elucidate important information like location of conduction block but also to study the interaction of the left and right ventricle.^{17-19,22}

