2.0 STUDY OBJECTIVES

The purpose is to prospectively study the feasibility to optimize configuration of CRT delivery for acute correction of electrical dyssynchrony using a noninvasive mapping of global electrical activation.

Study Hypothesis

Tailor-made configuration of CRT delivery is feasible and able to improve responder rate compare to single method of CRT delivery in candidates with known poor response to CRT.

Primary outcome measure

Responder rate of greater than 10% of LV end systolic volume reduction in patients undergoing tailor-made approach of CRT delivery at 6 months. The responder rate is to compare with pre-defined level of 40% for single method of CRT delivery namely biventricular pacing with LV lead in coronary sinus.

Secondary outcome measures

1. The acute electrical dyssynchrony indices of different methods of CRT delivery.
2. The hemodynamic responses of different methods of CRT delivery.
3. Procedure duration and implantation success rate of the optimal CRT delivery method as determined by the best improvement in electrical dyssynchrony indices.
4. Cine images (PA, LAO 30°, RAO 30°) and Chest X ray (PA view)
5. Peri-operative and 6 months follow-up complications rate:
 - a. Thromboembolic event
 - b. Dislodgement and migration of pacing leads
 - c. Phrenic nerve stimulation
 - d. Others
6. Echocardiogram parameters at baseline and 6 months: left ventricular systolic and diastolic volume, left ventricular ejection fraction, degree of mitral regurgitation, strain imaging.
7. NYHA class, 6 minute hall walk test and quality of life using Minnesota's questionnaire at baseline and 6 months.
8. Electrical parameters including threshold, sensitivity and lead impedance of pacing leads at implant and 6 months follow-up.

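### Ventricular electrical uncoupling has two incompatible formulas: a difference of means in words and a difference of ranges in parentheses

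*Combined protocol and SAP*

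**What the plan says.** Section 6.0, under noninvasive mapping of electrical activation, lists five dyssynchrony indices. Three of them matter here:

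- Item ii: "RVTAT is defined as the time difference between the earliest and latest site of activation on the RV ventricular epicardium".
- Item iii: "LVTAT is defined as the time difference between the earliest and latest site of activation on the LV ventricular epicardium".
- Item iv: "Ventricular electrical uncoupling (VEU) is defined as mean LV activation time minus mean RV activation time (LVTAT-RVTAT".

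The time at each site has a stated origin: "Local ventricular activation times will be defined as the onset of the QRS complex or the pacing spike to the maximal negative slope".

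The indices are used in two ways. First, they are an outcome. Secondary outcome 1 in Section 2.0 is "The acute electrical dyssynchrony indices of different methods of CRT delivery", and Section 1.0 says: "The acute change in electrical dyssynchrony indices will be compare between the optimal configuration and the conventional configuration". A significant difference there is to be read as evidence that an optimal configuration exists and that tailoring is feasible. Second, they guide treatment choice. Section 1.0 states: "The optimal configuration of CRT delivery is defined by that result in the greatest improvement of electrical dyssynchrony". Secondary outcome 3 likewise ties the optimal method to the best improvement in the indices, in the plural. No deciding index or weighting is named.

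**The concern.** A mean and a range answer different questions. The difference in mean activation time shows how late one ventricle is relative to the other. The difference in ranges shows whether activation is more spread out in one ventricle than in the other. Item iv presents the two as the same quantity.

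Two analysts could each follow item iv faithfully and report different values of VEU for the same map. If the parenthesis is programmed, the result labelled as uncoupling would not measure delay between the ventricles. It would also add nothing to the list, being simply item iii minus item ii. Section 1.0 names lack of ventricular uncoupling as a possible reason for non-response and wants mapping to show how the two ventricles interact. A difference in spread does not serve that aim.

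A smaller, related gap is that VEU is signed and the plan does not say what counts as improvement. Section 3.0 admits non-LBBB patients, and Section 1.0 suggests that His-bundle pacing may help "in patients with right bundle branch block (RBBB) pattern of conduction disturbance". Late-RV maps, with negative worded VEU, are therefore plausible.

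**Working it through.** The plan gives no VEU value, standard deviation or VEU-based sample size, so there is no figure to reproduce. The check is algebraic, followed by illustrations. All activation times below are assumed. They show that the formulas can diverge, not how often they do so in these patients.

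**Formulas**, with L and R the sets of LV and RV site times in one map:

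- Words: VEU(w) = mean(L) - mean(R)
- Parenthesis: VEU(p) = [max(L) - min(L)] - [max(R) - min(R)], from items ii and iii
- Item i: TAT = latest minus earliest site over both ventricles

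**Algebra.** Add a constant d to every LV time. Then mean(L) rises by d, so VEU(w) rises by d. Both max(L) and min(L) rise by d, so the range, and hence VEU(p), is unchanged. This holds for any shape of activation.

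**Illustrations.** Sites are evenly spaced, so each mean is the midpoint of the interval.

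1. Constant LV delay, with RV 0-60 ms and LV from d to 60+d ms:

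| d (ms) | VEU(w) = (30+d) - 30 | VEU(p) = 60 - 60 | TAT = 60+d |
|---|---|---|---|
| 10 | +10 | 0 | 70 |
| 20 | +20 | 0 | 80 |
| 30 | +30 | 0 | 90 |
| 40 | +40 | 0 | 100 |

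If the RV is delayed instead, VEU(w) is -10 to -40 ms and VEU(p) is again 0.

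2. Opposite sign, with LV 0-70 and RV 50-90 ms: VEU(w) = 35 - 70 = -35 ms; VEU(p) = 70 - 40 = +30 ms.

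3. Same sign, different size, with LV 0-100 and RV 0-60 ms: VEU(w) = 50 - 30 = +20 ms; VEU(p) = 100 - 60 = +40 ms.

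4. Two pacing settings with equal TAT of 100 ms:
   - A, LV 0-100 and RV 20-80: VEU(w) = 50 - 50 = 0; VEU(p) = 100 - 60 = +40 ms.
   - B, LV 0-70 and RV 30-100: VEU(w) = 35 - 65 = -30 ms; VEU(p) = 70 - 70 = 0.

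   Judged by the size of VEU alone, the words favour A and the parenthesis favours B.

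5. Direction of improvement, with LV 0-60 ms in both maps and RV moving from 40-100 to 10-70 ms: VEU(w) goes from 30 - 70 = -40 to 30 - 40 = -10 ms. Signed VEU rises by 30 ms while |VEU| falls by 30 ms. VEU(p) is 60 - 60 = 0 both times.

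**The case against.** The best defence is that the worded definition is explicit and comes first, so the parenthesis is a trailing slip that no competent analyst would program. That may be how it turns out, but the plan does not say which expression governs. LVTAT and RVTAT are defined terms, so reading them as shorthand for means would override the two items immediately above.

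Second, the blindness to a constant delay belongs to one version of one index. TAT over both ventricles registers the delay: it runs from 70 to 100 ms in illustration 1 and falls from 100 to 70 ms in illustration 5. Illustration 4 holds TAT equal by construction, and even there LVTAT differs (100 against 70 ms). This stands as a limit on the consequence, but it does not make the VEU formula right.

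Third, the primary endpoint, its test and its sample size do not use VEU, and values for reporting can be recomputed from the recorded maps. That also stands. An effect on the choice of configuration is possible but not shown, because no deciding index is named. That missing rule is a separate gap.

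Fourth, the direction of improvement is a separate omission, since the order of subtraction is given. This is fair: it is missing detail, not part of the contradiction. The remark on RBBB in Section 1.0 also does not describe the enrolled population; that such patients can enter follows from the non-LBBB criterion in Section 3.0.

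**Conclusion.** The concern holds: item iv is wrong as written. It equates two different quantities, and the range version cannot register a constant delay of one ventricle. That conclusion is exact and needs no data. The sizes shown (0 against up to 40 ms, and -35 against +30 ms) rest on assumed activation times and say nothing about frequency in this population.

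The certain consequence is an ambiguous VEU result under secondary outcome 1 and in the planned comparison of optimal with conventional pacing. An influence on which configuration is implanted is possible only. The primary comparison of the responder rate with 40% is not computed from VEU. The point should be corrected, but it does not threaten the main test.

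**What to change.** In item iv, delete the parenthesis and keep the worded definition: the mean of LV activation times minus the mean of RV activation times over the mapped sites. If symbols are wanted, use new ones for the two means so that LVTAT and RVTAT keep their meaning as ranges. The sponsor should confirm that this is the intended index.

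Add one sentence on direction, for example that change in |VEU| will be reported alongside signed VEU.

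The cost is a one-line correction and one sentence. VEU values already obtained can be recomputed from stored maps. If VEU has contributed to any choice of configuration, recomputation cannot revise an implant already made, so the correction should come before further maps are used for that purpose.

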3.0 PATIENT SELECTION CRITERIA

Inclusion criteria:

Adult (aged 18 or above) of both sexes

Ischemic or non-ischemic cause of heart failure

QRS duration > 120 ms, non -LBBB type of conduction disturbance

NYHA class III or above

Sinus rhythm

Informed consent by the patient

Already received stable dose of guideline directed medical therapy for at least 3 months

Exclusion criteria

LBBB* patients

Pregnant women

Participation in another study

Patient with contraindication to left ventricle catheterization by a retrograde aortic approach (eg mechanical aortic valve, severe aortic stenosis and aortic dissection)

*The definitions of LBBB (QRS duration \geq 130 ms; QS or rS in lead V1; broad R waves in leads I, aVL, V5, or V6; and absent q waves in leads I, V5, and V6).

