5.0 STATISTICAL CONSIDERATION

Hypothesis

The null and alternative hypotheses are as follows:

H0: The responder rate of tailor-made approach \leq 40%

HA: The responder rate of tailor-made approach $>$ 40%

Sample size was calculated employing binomial methods with the following assumptions were used:

Expected responder rate for tailor-made approach =60%

Historical control responder rate =40%

Test significance level (a) = 0.05 (1-sided)

Power= 80%

Based on the above assumptions, the sample size was calculated as 77. Accounting for the attrition of 20%, the total required sample size is 93 patients with device implanted.

Statistical method for additional analysis

All continuous data will be summarized with the number of non-missing data, mean \pm standard deviation, median and range (minimum – maximum). T test will be used for the comparison between the groups. In case the assumption for t test is violated, then the equivalent nonparametric test, such as Wilcoxon rank sum test, Kolmogorov-smirnov test, will be used instead. The normality assumption will be tested by the normality test with the aid of QQ plot.

All categorical data will be tabulated with number of occurrence and percentage. Chi-square test will be used for the comparison between the groups. In case the expected counts in each cell is less than 5, then Fisher's exact test will be used instead.

Procedures for reporting any deviation(s) from the original statistical plan

Any deviations from the statistical analysis plan will be documented.

The treatment of missing, unused or spurious data, including drop-outs and withdrawals.

No imputation techniques will be used.

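### The acute study places pacing leads at two endocardial LV sites that none of the 8 listed configurations and none of the 4 implant routes uses

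*Combined protocol and SAP*

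**What the plan says.** Section 6.0 (Placement of electrophysiology catheters for CRT delivery) names eight positions for pacing leads:

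- high right atrium
- His bundle
- RV apex
- high RV septum
- coronary sinus, posterior/lateral branch
- coronary sinus, anterior branch
- lateral LV endocardium
- septal LV endocardium

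The sentence gives its own purpose. It ends with the "lateral and septal region of endocardial LV in order to deliver CRT in 8 different configurations as stated below". Four numbered headings follow, two of them with sub-items. Section 6.0 (Implantation of CRT device) then gives four implant routes under matching numbers.

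Section 1.0 defines the optimal configuration as the one that most improves electrical dyssynchrony, and that configuration is then implanted. It mentions endocardial LV pacing only as background and notes that long-term clinical results against epicardial pacing are lacking.

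**The concern.** The sentence is an operative instruction for an invasive step on the left side of the heart, and the reason it gives for that step does not cover two of the sites. If operators follow it, each patient in the acute study has pacing leads taken to two LV endocardial positions from which nothing listed is paced, measured or implanted. A research-only invasive step needs a stated purpose. Section 6.0 itself lists perforation, tamponade, thromboembolism and death as possible events of the acute study.

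The number of patients concerned is that of the acute study, which precedes implant. Section 5.0 says "the total required sample size is 93 patients with device implanted".

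**Working it through.** **Step 1: reproduce the stated count.** Taking the sub-items under the His-bundle and multi-point headings, and treating the sinus-rhythm and AF lines as add-ons to the His-bundle items, the list gives 1 + 1 + 3 + 3 = 8. This matches the stated 8, so the list is complete without an endocardial item.

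**Step 2: LV site of each configuration.**

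| Configuration | LV site | Endocardial LV? |
|---|---|---|
| 1 Conventional biventricular | coronary sinus, lateral/posterior | no |
| 2 Latest-activation site | coronary sinus, nearest reachable point | no |
| 3i His tip to RV lead | none | no |
| 3ii His tip to LV lead | coronary sinus, lateral/posterior | no |
| 3iii His tip to His proximal pole | none | no |
| 4i Two RV leads, one LV lead | coronary sinus, posterior/lateral | no |
| 4ii One RV lead, two LV leads | coronary sinus, posterior/lateral and anterior | no |
| 4iii One RV lead, quadripolar LV lead | coronary sinus, posterior/lateral | no |

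Result: 0 of 8.

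**Step 3: implant routes.**

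- Route 1 is the conventional system.
- Route 2 is headed as epicardial.
- Route 3 is a His lead with an LV lead, preferably in a posterolateral coronary sinus branch.
- Route 4 combines a septal RV lead with an LV lead, or an anterior with a posterior/lateral LV lead, or uses one quadripolar lead.

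Result: 0 of 4.

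**Step 4: uses of each named position** (configurations that name it).

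- His bundle: 3 (3i to 3iii).
- RV apex: 4 (1, 4i to 4iii), plus the sinus-rhythm add-on. Items 2 and 3i also use an RV lead without naming its site.
- High RV septum: 1 (4i).
- Coronary sinus, posterior/lateral: 5 (1, 3ii, 4i to 4iii).
- Coronary sinus, anterior: 1 (4ii).
- High right atrium: 0 as a pacing site. Atrial sensing for the VDD mode is a plausible role, but that is an inference.
- Lateral LV endocardium: 0.
- Septal LV endocardium: 0.

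Six of the eight positions have a stated or plausible role. Two have none.

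**Step 5: other possible reasons for the leads.**

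- *Pressure.* LV dP/dt comes from a separate micromanometer in the LV cavity.
- *Mapping.* The activation maps are noninvasive and the indices are epicardial. The intra-LV index, for example, is the "standard deviation of activation times at 500 sites on the LV epicardium".
- *Pacing settings.* The rule that "the output will be set at twice the capture threshold" applies while CRT is being delivered, so it gives no task to a lead outside every configuration.
- *AF add-on.* The words "together with RV bipolar and LV bipolar pacing" name no LV site. The AF implant text keeps the LV lead where it is for sinus rhythm, and Section 3.0 requires sinus rhythm for entry.

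**The case against.** The strongest reply is that this is a stray phrase and not a real exposure. The sentence ties the leads to the configurations stated below it. Those configurations are complete at 8 without an endocardial site, and no implant route would use one, so an operator working from the list has no endocardial pacing to perform. Much of the risk is also already handled. The LV is entered anyway for the micromanometer. Section 3.0 excludes any "Patient with contraindication to left ventricle catheterization by a retrograde aortic approach". Section 6.0 discloses perforation, thromboembolism and pacing-catheter risk in general terms.

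Most of this stands. It limits the concern to an unquantified increment and favours deletion as the default. It does not remove the mismatch, because the text still says that the leads will be placed.

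A reader might infer more in two ways, and the documents support neither.

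- *A sized safety harm.* One could multiply the two sites by the planned number of patients. That would count positions, not catheters or events, since one catheter could be moved between sites. No risk per placement is given, so the product does not measure harm.
- *A deliberate endocardial arm left out of the list.* Section 1.0 discusses endocardial pacing, and an endocardial winner would have no implant route. But the stated 8 is met without one. The item "Figure 1. Study Flow Chart" is not shown in the available text. It could bear on intent, but it would not reconcile the placement sentence with the list.

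**Conclusion.** The point holds as an internal inconsistency in an invasive instruction: 2 of 8 named lead positions are used by 0 of 8 configurations and 0 of 4 implant routes, and no other stated measurement needs them. Confidence is high for the mismatch. It is not high for actual patient exposure, which depends on whether operators follow the sentence literally.

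If they do, the added risk is that of endocardial LV pacing-lead placement beyond the LV access needed for pressure measurement. The documents give no figure for it, and none is offered here.

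The responder endpoint and its test against 40% do not depend on these leads, so the point has no bearing on the statistical design. It should be corrected because the step carries some risk and has no stated use, and the correction is nearly free.

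**What to change.** Ask the investigators to confirm that no endocardial LV configuration is intended. On that confirmation, delete the lateral and septal endocardial LV sites from the placement sentence in Section 6.0. Six positions then remain: high right atrium, His bundle, RV apex, high RV septum, and the posterior/lateral and anterior coronary sinus branches. The 8 configurations stay as listed.

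The cost is one query and one deletion. The change removes an invasive step, leaves all 8 listed configurations deliverable and alters no endpoint or analysis.

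If the investigators say that an endocardial configuration is intended, deletion is wrong. They would need a substantive amendment that adds the configuration to the list and gives it an implant route. The documents do not allow that cost to be sized.
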